1. The baseline visit of Study A3921288 is the same visit as the last visit in Study A3921139. All procedures done at the last visit in A3921139 for subjects enrolled into Study A3921288 will be used as the baseline data for Study A3921288. Procedures listed as OLE procedures will NOT BE REPEATED at baseline of Study A3921288. Only those procedures marked with an 'X' will be performed at the baseline visit of Study A3921288.
2. Medical history from Study A3921139, including resolved adverse events (AEs) will be used for Study A3921288. Ongoing AEs from Study A3921139 will be followed throughout Study A3921288.
3. The targeted physical examination consists of weight, general appearance, and examinations of eyes, mouth, lungs, heart, abdomen, musculoskeletal, extremities, skin and lymph nodes.
4. Urine β -hCG to be performed only for females of childbearing potential. Pregnancy testing may be performed more frequently per local regulations.
5. Stool samples will be collected at baseline and at each scheduled study visit to measure fecal calprotectin (see [Section 7.3.3.1](#)). In addition, stool samples should be obtained at the time of worsening disease and/or flare when possible.

6. Tuberculosis (TB) screening will be conducted at Month 12 using Quantiferon-TB[®] Gold Plus test (QFT) only for subjects in those countries in which TB prevalence has been reported at a rate of >50 cases per 100,000 persons (see [Section 7.3.3.2](#)). All subjects with positive results must have chest radiograph performed. Note: QFT should not be performed in subjects who had positive result during prior testing (screening visit in Induction Study A3921094 or A3921095 or prior annual visits in Study A3921139) and/or previously received adequate treatment for TB.
7. Safety monitoring for a subset of subjects in Japan only. See [Appendix 4](#) for details.
8. Flexible sigmoidoscopy/colonoscopy (if preferred) will be performed at Month 6, Month 18 and at ET for all subjects. In order for a subject to be eligible for Study A3921288, they must have an endoscopy performed in Study A3921139 ≤6 months prior to baseline of Study A3921288 with an endoscopic subscore of 0 or 1. Mayo endoscopic subscore will only be assessed by local site read.

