6.2. Study Period

6.2.1. Baseline (Visit 1)

The baseline visit of Study A3921288 is the same visit as the last visit in Study A3921139. All procedures done at the last visit in A3921139 for subjects enrolled into Study A3921288 will be used as the baseline data for Study A3921288.

The study investigator or appropriate delegate at the site will discuss with each subject the nature of the study, its requirements, risks and its restrictions. Written informed consent must be obtained prior to performing any protocol-specific procedures.

The following procedures will be performed:

- Obtain informed consent.
- Review medical history and concomitant medications. Medical history from Study A3921139 will be used as baseline for Study A3921288. Resolved AEs occurring in Study A3921139 will be captured as part of Baseline Medical History, while ongoing AEs from Study A3921139 will be followed throughout Study A3921288. Ongoing concomitant medications from Study A3921139 will be recorded in Study A3921288.
- Demography, including birth date, sex/gender, ethnicity and race will be collected at the Baseline/Day 1 visit and provided in the case report form as allowed by local regulations.
- Collect stool sample for fecal calprotectin. If a sample cannot be collected at the visit, provide subject with stool collection kit to obtain stool sample at home. Subjects should be instructed to make all efforts to collect the baseline sample as soon as possible, but no later than 7 days of the baseline visit. The stool sample should be returned within 24 hours of collection.
- Provide subject with stool sample collection kit to obtain stool sample at home to be returned for the Month 1 study visit.
- Risk factor check for pulmonary embolism, per Amendment 2.
- Confirmation of all inclusion/exclusion criteria.
- Randomization.
- Investigational product dispensing.
- Subjects will be reminded of instructions for using the phone based bowel movement (BM) diary. Subjects should start completing the BM diary daily approximately 7 days prior to their next scheduled visit. Study site staff should contact the subjects 7 days prior to the scheduled visit to ensure compliance. In addition, subjects should be instructed to start completing the BM diary whenever he/she experiences any worsening of UC symptoms anytime during the study.
- Contraception check for females of childbearing potential.
- Adverse event monitoring.

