7.3.4. Infections

Subjects will be monitored for development of infection. If high-risk behaviour(s) or environmental exposures are identified, subjects may be tested to provide evidence that pre-specified infections (eg, HIV, HCV, HBV) are not present. All treated infections occurring during the study should be cultured if feasible and the results (eg, any identified organisms or absence of growth) recorded in the CRF.

Treated infections will be further classified as serious or non-serious. Serious infections are treated infections that:

- Require parenteral antimicrobial therapy; or
- Require hospitalization for treatment; or
- Meet other criteria that require the infection to be classified as a serious adverse event (SAE).

A subject who experiences a treated serious infection should be discontinued from the study. A serious infection should be reported as a SAE and should be listed as the reason for discontinuation in the CRF. All serious infections occurring during the study should undergo appropriate laboratory investigations, including culture, and the results (eg, any identified organisms or absence of growth) recorded in the CRF.

Subjects who experience non-serious infections that require treatment may have their study drug temporarily discontinued during treatment (see [Section 5.12](#)). Temporary discontinuation of study drug should be recorded in the CRF.

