8.3. Severity Assessment

If required on the AE page of the CRF, the investigator will use the adjectives MILD, MODERATE, or SEVERE to describe the maximum intensity of the AE. For purposes of consistency, these intensity grades are defined as follows:	
MILD	Does not interfere with subject's usual function.
MODERATE	Interferes to some extent with subject's usual function.
SEVERE	Interferes significantly with subject's usual function.

Note the distinction between the severity and the seriousness of an AE. A severe event is not necessarily an SAE. For example, a headache may be severe (interferes significantly with the subject's usual function) but would not be classified as serious unless it met one of the criteria for SAEs, listed above.

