3.5. Safety Endpoints

The safety endpoints in this study include:

- Incidence and severity of adverse events (AEs).
- Incidence and severity of clinical laboratory abnormalities, and change from baseline in clinical laboratory values.
- Incidence of vital sign abnormalities and change from baseline in vital signs.

- Incidence of clinically significant changes in physical examinations from baseline.
- Safety events of interest including adjudicated safety events (eg, opportunistic infections, malignancy, gastrointestinal perforation, hepatic events, and cardiovascular events).

An adverse event is considered treatment emergent relative to a given treatment if the event starts after the first dose. The first dose is defined as the first dose in Study A3921288.

A 3-tier approach will be used to summarize AEs. Under this approach, AEs are classified into 1 of 3 tiers. Different analyses will be performed for different tiers (See [Section 6.6.1](#)).

Tier-1 events: These are pre-specified events of clinical importance and are maintained in a list in the product's Safety Review Plan.

Tier-2 events: These are events that are not tier-1 but are "common". A MedDRA Preferred Term is defined as a tier-2 event if there are at least 4 in any treatment group.

Tier-3 events: These are events that are neither tier-1 nor tier-2 events

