6.6.1. Adverse Events

The analyses of adverse events under the 3-tier approach described in [Section 3.5](#) is considered exploratory. There will be no adjustment for multiple comparisons or stratification factors in the analyses. For tier-1 events, the proportion of AEs observed in each group will be presented along with the point estimates and associated 95% confidence intervals of the risk difference, and p-value for dose comparison or regimen comparison using the exact methods proposed by Chan and Zhang (1999)² described in [Section 5.2.5](#). For tier-2 events, the proportion of AEs observed in each group will be presented along with the point estimates and associated 95% confidence intervals of the risk difference using the normal approximation for the difference in binomial proportions. In case of zero event rate for tier-2 events in any of group, the 95% confidence intervals will not be computed. AEs will be arranged in the output sorted in descending point estimate of the risk difference within system organ class. Tier 3 AEs will not be summarized separately, they are included

in the overall standard AE summary. Footnotes in the outputs will include the methods used to derive any p-values and confidence intervals as per Pfizer standards.

A listing of subjects with dose reduction due to PE risk factors will be provided.

Incidence Rates (IR) of Adverse Events of Special Interest will be provided. Confidence intervals (95%) will be computed using the exact Poisson method.

For regimen groups, IR will be calculated only for adverse event data for events of special interest only. The numerator will be the number of unique subjects with a treatment emergent event as defined above during the interval from the first dose in A3921288 study to last dose of tofacitinib + 28 days at risk period. The denominator of the incidence rate is person time accruing from the subject's first dose to last dose + 28 days, or to the date of the first event, whichever occurs earlier. For a subject who died, the time will be the minimum of (the date of the last dose + 28 days, or death date).

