For dose groups, IR will be calculated only for adverse events of special interest only. The numerator will be the number of unique subjects with a treatment emergent event as defined above during the interval from the first dose in A3921288 study to dose adjustment for dose escalated or dose reduced subjects otherwise to last dose + 28 days at risk period. The denominator of the incidence rate is person time accruing from the subject's first dose to day of dose escalation, or the first dose to day of dose reduction, or last dose + 28 days, or to the date of the first event, whichever occurs earlier. For a subject who died, the time will be the minimum of dose escalation day, dose reduction day, the day of the last dose + 28 days, or death day.

However, for mortality (death), malignancies (including NMSC), malignancies (excluding NMSC) and MACE related endpoints, all events regardless of their onset within 28 days or beyond after the last dose of tofacitinib will be included. The concept of 28 days is applied to subjects without events that discontinued or completed the study.

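### Adverse events carried in from the parent study that become serious after randomisation are left out of the special-interest incidence rates, unless sites enter them as new events

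*SAP*

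**What the plan says.** - **Definition (SAP 3.5).** "An adverse event is considered treatment emergent relative to a given treatment if the event starts after the first dose". The next sentence fixes the reference point: "The first dose is defined as the first dose in Study A3921288". There is no clause for an event that is already present and then worsens or becomes serious.
- **Carried-over events (Protocol 6.2.1).** The baseline visit is the last visit of Study A3921139. Resolved events from that study become medical history, while "ongoing AEs from Study A3921139 will be followed throughout Study A3921288".
- **Incidence rates (SAP 6.6.1).** For the regimen groups, "The numerator will be the number of unique subjects with a treatment emergent event as defined above". The dose-group paragraph uses the same restriction. Rates are planned only for events of special interest.
- **Exception (SAP 6.6.1).** For death, malignancy and MACE, "all events regardless of their onset within 28 days or beyond after the last dose of tofacitinib will be included".
- **Severity (Protocol 8.3).** Where the CRF asks for it, intensity is recorded as "MILD, MODERATE, or SEVERE to describe the maximum intensity of the AE".
- **Serious events.** Protocol 8.1.4.1 and 8.1.4.2 require every SAE in the active collection period to be reported to the sponsor's safety function and recorded on the CRF. On infections, Protocol 7.3.4 adds: "A serious infection should be reported as a SAE and should be listed as the reason for discontinuation in the CRF".

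**The concern.** Every subject enters directly from a parent study after at least two consecutive years on 10 mg BID, so some will arrive with adverse events still open. The randomised contrast is a step down in dose against staying on the entry dose. A change in an existing event is one way in which a difference between doses could appear.

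Under the onset rule, an event that began before the first dose here can never become treatment-emergent. An infection open at rollover that later leads to hospital admission would be an SAE and a reason for discontinuation. If it keeps its parent-study start date, it would still be absent from any rate or table built on the definition. Long-term safety was a stated reason for extending treatment to 42 months, so the special-interest rates by dose are among the outputs that readers will use most.

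**Working it through.** The plan gives no figure to reproduce. The check is mainly of text, followed by arithmetic for scale.

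**Step 1: is there another route to treatment-emergent status?** No. SAP 3.5 offers onset after first dose and nothing else. The exception for death, malignancy and MACE extends the window after the last dose and does not touch onset before the first dose.

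**Step 2: would a worsened event get a new start date?** The documents do not say. They say that ongoing events are followed. No section tells sites to close the record and open a new one on worsening, and a single maximum intensity per event suggests one continuing record. That the parent-study start date is kept is therefore an inference.

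**Step 3: which outputs depend on the definition?**

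| Output | Basis stated in the SAP | Carried-over event that becomes serious |
|---|---|---|
| Special-interest incidence rates, regimen and dose groups (6.6.1) | Treatment-emergent as defined | Left out, if no new entry is made |
| Tier-1 and tier-2 tables (6.6.1) | Adverse events observed | Not determined by the text |
| Laboratory values, vital signs, physical examination (3.5) | Mostly change from baseline | Any measurable change remains visible |
| SAE recording and reporting (Protocol 8.1.4) | All SAEs in the collection period | Captured |

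**Step 4: scale.** Inputs are 65 per arm (Protocol 9.1) and 138 enrolled at Amendment 2 (Protocol 9.1), which at 1:1 is 138/2 = 69 per arm. Treatment lasts 42 months, or 3.5 years. Mean exposure of 1.5 years is my assumption, to show a range.

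- One subject: 1/65 = 1.5 points; 1/69 = 1.4 points.
- Tier-2 threshold of 4 in any group, taken as subjects: 4/69 = 5.8% and 3/69 = 4.3%. If the tier tables are run on treatment-emergent events, and the other arm is also below 4, one exclusion moves a term out of tier 2 and its confidence interval is lost.
- Rates: x/PY × 100. The exact Poisson 95% limits are χ²(0.025; 2x)/2 and χ²(0.975; 2x+2)/2, each divided by PY. Treatment time only is used, without the 28-day tail.

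| Person-years per arm | 1 event, per 100 PY (95% CI) | 0 events, per 100 PY (95% CI) |
|---|---|---|
| 69 × 3.5 = 241.5 (complete follow-up) | 0.41 (0.01 to 2.31) | 0 (0 to 1.53) |
| 69 × 1.5 = 103.5 (assumed) | 0.97 (0.02 to 5.38) | 0 (0 to 3.56) |

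The number of events ongoing at entry is not given, so the actual effect cannot be computed.

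**The case against.** The strongest case on the other side has five parts.

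- **The rule is deliberate.** The SAP change log says the definition was updated to a new standard, and both documents place safety summaries under the sponsor's data standards. This stands, and it is why the definition should be kept and supplemented. It does not show that an onset-only count is sufficient for a rollover population.
- **The start-date premise is inferred.** CRF completion rules outside these documents may require a new entry. Protocol 8.2.1 also lists worsening of underlying disease as an example of an adverse event. This stands as a condition: if worsening is entered as a new event, it is counted.
- **The special-interest list is not in the SAP.** The examples in SAP 3.5, such as malignancy or perforation, would usually be new diagnoses with onset on study. Whether a serious infection would enter a rate at all cannot be confirmed. This stands, and the infection example is only an illustration.
- **The effect lies within the imprecision.** The intervals for one event and for none overlap widely, allocation is randomised, the rule applies to both arms, and the tiered analyses are labelled exploratory. This stands against any claim of bias. It does not explain why an on-study serious event should go uncounted.
- **Serious events are captured elsewhere.** This stands, and it makes a supplementary count feasible.

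A reader might infer that worsened events disappear from all safety tables. The documents do not support that: the tier tables refer to observed events, and SAEs are recorded regardless of when the underlying event began.

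**Conclusion.** The point holds in a limited form. As written, the special-interest incidence rates omit an adverse event that was ongoing at the first dose and became serious afterwards, as does any other table run on treatment-emergent events. This rests on one assumption, that sites do not enter the worsening as a new event; the documents contain no rule either way.

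The omission is from summaries and rates, not from safety surveillance. Each omitted subject is worth about 1.5 percentage points of an arm, or 0.41 to 0.97 per 100 person-years under the exposure assumptions above. A new diagnosis, a complication or a UC flare in a subject who entered in remission starts on study and is counted.

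It may be tempting to conclude that the rule hides a safety difference between doses, or favours one of them. The documents do not support that, because neither the number nor the direction of affected events can be known from them. This is a small, worthwhile improvement, not a flaw that undermines the safety analysis.

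**What to change.** 1. Keep the definition in SAP 3.5. Add to SAP 3.5 and 6.6.1 a supplementary row, by dose group and by regimen group, that counts treatment-emergent events plus any event ongoing at the first dose in Study A3921288 that becomes serious after it. Use the SAE onset date as the event date, end person-time there, and apply the at-risk periods already set for each grouping, including the cut at dose change for dose groups.
2. State whether the tier tables use treatment-emergent events or all observed adverse events.
3. Label the row as added after the Month 6 unblinding. SAP 7.1 has the sponsor's team unblinded from that analysis onwards, and SAP 5.3.3 says all subjects had completed Month 6 when version 2 was finalised.

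The cost is one SAP sentence for the row, a clarification for the tier tables and some programming, using data already collected. The sponsor should first confirm that the SAE onset date gives the date on which the event became serious.

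The downside is that an increase in severity without seriousness stays outside the row, because maximum intensity does not show when the increase occurred. A wider clause covering all worsening could not be applied reliably to past events. A new CRF instruction at this stage would make ascertainment differ before and after the change.

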8.2. Definitions

8.2.1. Adverse Events

An AE is any untoward medical occurrence in a study subject administered a product or medical device; the event need not necessarily have a causal relationship with the treatment or usage. Examples of AEs include, but are not limited to:

- Abnormal test findings;
- Clinically significant signs and symptoms;
- Changes in physical examination findings;
- Hypersensitivity;

- Progression/worsening of underlying disease;
- Drug abuse;
- Drug dependency.

Additionally, AEs may include signs and symptoms resulting from:

- Drug overdose;
- Drug withdrawal;
- Drug misuse;
- Drug interactions;
- Extravasation;
- Exposure during pregnancy (EDP);
- Exposure via breastfeeding;
- Medication error;
- Occupational exposure.

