2.1. Study Objectives

Primary Objective

- To evaluate the efficacy and safety of tofacitinib in subjects in stable remission on 10 mg BID who decrease the dose to and remain on 5 mg BID (“5 mg BID dose group”) compared to subjects remaining on 10 mg BID.

Secondary Objectives

- To evaluate the efficacy and safety of tofacitinib in subjects in stable remission on 10 mg BID who decrease the dose to 5 mg BID with option for dose escalation for flare (“flexible dosing regimen”) compared to subjects staying on 10 mg BID.
- To evaluate the efficacy and safety of the subset of subjects in stable remission on 10 mg BID who have flare after dose decrease to tofacitinib 5 mg BID and are re-treated with 10 mg BID.

[figure not shown]

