5.2. General Methods

For the primary objective, analyses will be performed for comparisons of the following two dose groups:

- Tofacitinib 10 mg BID dose group: subjects who are initially assigned to tofacitinib 10 mg BID at randomization
- Tofacitinib 5 mg BID dose group: subjects who are initially assigned to tofacitinib 5 mg BID at randomization, regardless of whether the dose is escalated back to tofacitinib 10 mg BID or not (Data collected after the dose escalation from tofacitinib 5 mg BID to 10 mg BID will not be included in the analyses.)

For the first secondary objective, analyses will be performed for comparisons of the following two regimen groups:

- Tofacitinib 10 mg BID regimen group: subjects who are initially assigned to tofacitinib 10 mg BID at randomization.
- Tofacitinib 5 mg BID regimen group: subjects who are initially assigned to tofacitinib 5 mg BID at randomization, staying on tofacitinib 5 mg BID or having dose escalation from tofacitinib 5 mg BID to 10 mg BID. Data collected after the dose escalation will be included in the analyses.

For the second secondary objective, summary descriptive statistics will be reported for the subgroup of subjects who are initially assigned to tofacitinib 5 mg BID and later are re-treated with tofacitinib 10 mg BID based on the observed case data using the original windowing rules. In addition, the efficacy data after the dose escalation will be summarized using the new windowing rule by resetting the baseline (Day 0) at the dose escalation time.

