6.6. Safety Summaries and Analyses

The safety data will be summarized in accordance with Pfizer Data Standards.

All safety data will be summarized descriptively by dose group, regimen group and the subgroup of subjects who are initially assigned to tofacitinib 5 mg BID and later are retreated with tofacitinib 10 mg BID in the safety analysis set.

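### The adverse event summary for subjects re-treated with 10 mg BID is not cut at dose escalation, so no specified summary isolates safety after re-treatment

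*SAP*

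**What the plan says.** The second secondary objective (SAP 2.1, Protocol 2.1) covers both efficacy and safety in the subjects who "have flare after dose decrease to tofacitinib 5 mg BID and are re-treated with 10 mg BID".

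For adverse events, SAP 3.5 states: "An adverse event is considered treatment emergent relative to a given treatment if the event starts after the first dose". The next sentence fixes the anchor: "The first dose is defined as the first dose in Study A3921288".

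SAP 6.6 names the re-treated subgroup as one of three groupings for safety: "All safety data will be summarized descriptively by dose group, regimen group and the subgroup of subjects" re-treated with 10 mg BID. SAP 5.2.5 repeats this on observed-case data. Neither section limits the subgroup's data to the time after escalation.

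For the same subgroup, SAP 5.2 plans two views. The first is descriptive statistics for those "re-treated with tofacitinib 10 mg BID based on the observed case data using the original windowing rules". The second is an addition confined to efficacy: "the efficacy data after the dose escalation will be summarized using the new windowing rule by resetting the baseline (Day 0) at the dose escalation".

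Protocol 8.2.1 lists "Progression/worsening of underlying disease" among its examples of adverse events.

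**The concern.** A reader of the re-treatment safety table will want to know what happened to subjects once they were back on 10 mg BID. Under the SAP 3.5 anchor, the table also counts everything that began on 5 mg BID before escalation. The sponsor provided a post-escalation view for efficacy; safety stands in the same objective and has none for adverse events.

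Two features make the mixing matter. Every member of the subgroup has a 5 mg period first, because Protocol 5.11 bars escalation for flare before the Month 1 visit. And every member has a disease worsening that began before re-treatment, because flare must be confirmed before the dose is changed. If the site enters that worsening as an adverse event, an event that qualified the subject for the subgroup appears as treatment-emergent in the table meant to describe re-treatment. Dose is relevant to safety here: Protocol 1.2 reports a dose-dependent rate of herpes zoster.

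**Working it through.** The plan gives no figure for this subgroup, so there is nothing to reproduce. The check is mainly textual.

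**1. Which period does each specified adverse event summary cover for a subject who goes from 5 mg to 10 mg?**

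| Summary | Events before escalation | Events after escalation | Source |
|---|---|---|---|
| 5 mg dose group | counted | excluded | SAP 5.2.5, 5.3.2, 5.3.3, Table 2 |
| 5 mg regimen group | counted | counted, pooled | SAP 5.2.5, 5.3.2, 5.3.3, Table 2 |
| Re-treated subgroup | counted | counted, pooled | SAP 3.5, 5.2.5, 6.6 |

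No row excludes the first period and counts the second. The dose-change rules in SAP 5.3.3 and Table 2 are written for dose and regimen groups only. So are the incidence-rate rules in SAP 6.6.1. The subgroup therefore falls back on the general anchor in 3.5.

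**2. Can the triggering flare be counted?** Entry requires stable remission up to baseline (Protocol 4.1), and flare is confirmed before any dose adjustment (Protocol 5.11). The qualifying flare therefore begins after the first study dose and before re-treatment. Protocol 8.2.1 allows worsening disease to be recorded as an adverse event. Protocol 1.2 shows that this happened in the programme: colitis ulcerative was among the most frequent treatment-emergent events in the maintenance study. Inclusion is possible, but it depends on site recording.

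**3. How much time is mixed?** Inputs: Month 42 target Day 1260 and 30-day months (SAP Appendix 1), and 28 days after the last dose (SAP 6.6.1). Assumption: the subject stays on treatment to Day 1260. At-risk time is 1260 + 28 = 1288 days, and the share before escalation at Month m is 30m/1288:

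- Month 1: 30/1288 = 2.3%
- Month 6: 180/1288 = 14.0%
- Month 18: 540/1288 = 41.9%
- Month 30: 900/1288 = 69.9%

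**4. What could that do to a reported proportion?** Assume a constant event rate r per person-year, leaving the flare aside. The proportion with an event is 1 − exp(−rT), with T = 1288/365.25 = 3.53 years from the first dose, or (1288 − 30m)/365.25 years from escalation.

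| r (assumed) | From first dose | From escalation at Month 6 | Month 18 | Month 30 |
|---|---|---|---|---|
| 0.05 | 16.2% | 14.1% | 9.7% | 5.2% |
| 0.20 | 50.6% | 45.5% | 33.6% | 19.1% |

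The distortion is slight for early escalation and large for late escalation. The documents do not say when subjects escalated.

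**The case against.** The case on the other side has several parts, and some of it stands.

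- **The whole-course view is intended.** The objective speaks of the safety of a subset of subjects, and a summary over the whole study responds to those words. SAP 5.2 does the same for efficacy before adding the post-escalation view. This stands: the whole-course table is not an error and should not be replaced. What is missing is the second view. A reader might infer that the safety plan cannot address the objective at all; the text does not support that.
- **By-visit safety data may already be re-baselined.** Appendix 1 applies its windows to efficacy and safety data summarised by visit, and its re-treatment table takes the escalation day as baseline. SAP 3.4 permits another baseline where one is stated. So it would be too strong to infer that no safety data are reset. But SAP 5.2 restricts the reset to efficacy, so the two places disagree. Adverse event counts are not by-visit summaries, and Appendix 1 does not reach them.
- **The flare is not included by construction.** Flare is captured separately through subscores and endoscopy, and Protocol 8.2.2 excludes protocol-specified dose adjustments from one of its triggers for recording abnormal findings. A reader might infer that all members carry the flare as an adverse event. That is only an upper bound, and the documents do not show how often it is recorded.
- **No incidence rate is planned for this subgroup.** This stands. The shares above illustrate at-risk time; they do not correct a planned rate.
- **The dose-group and regimen-group tables can be compared.** Subtracting one from the other recovers subjects whose first event of a given type came after escalation. It does not recover subjects who had the event both before and after, so it is not a re-treatment summary.
- **The stakes are modest.** The subgroup summary is descriptive, SAP 5.1 tests no formal hypotheses, and SAP 6.6.1 calls the tiered adverse event analyses exploratory. Sponsor data standards, which cannot be seen here, might add a table. None of this supplies the missing rule.

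**Conclusion.** The point holds for adverse events. Under SAP 3.5, 5.2.5 and 6.6 as written, the re-treated subgroup's table pools events on 5 mg before escalation with events on re-treatment, and it may include the triggering flare. No specified adverse event summary isolates the period after re-treatment. For by-visit laboratory and vital-sign data, the finding is narrower: SAP 5.2 and Appendix 1 need to be reconciled.

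The size cannot be fixed from the documents. With treatment to Day 1260 plus 28 days, about 2% to 70% of a subject's at-risk time precedes escalation for escalation between Month 1 and Month 30. A reader might settle on about half, by assuming escalation midway through the study; nothing in the documents supports one value over another.

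The primary endpoint and the comparisons of dose and regimen groups are unaffected. The Month 6 analysis is for dose groups only (SAP 7.1), so the gap concerns the final analysis.

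**What to change.** Keep the whole-course table. In SAP 3.5, 5.2.5 and 6.6, add for the re-treated subgroup:

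1. A post-escalation adverse event summary counting events that start on or after the first dose following escalation.
2. A stated end of the risk period: the earlier of any later dose reduction for pulmonary embolism or venous thromboembolism risk factors, or last dose + 28 days. This follows the dose-group convention in SAP 6.6.1 and keeps the 5 mg to 10 mg to 5 mg sequence in Table 2 from mixing doses again. State whether the 6.6.1 exception for deaths, malignancies and MACE also applies.
3. A separate display of events before escalation, so that a recorded triggering flare is visible as such.
4. If an incidence rate is produced for this subgroup, person-time starting at escalation.

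Reconcile SAP 5.2 with Appendix 1 by stating that the escalation-day baseline also applies to by-visit laboratory and vital-sign summaries. Align the day label at the same time, since 5.2 calls the escalation day Day 0 and Appendix 1 calls it Day 1.

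The cost is one definition, one derived flag and one extra descriptive table. Onset dates and the escalation day are already used elsewhere in the SAP, so no new data are needed.
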